7.3 Duration of Participation

Describe how long subjects will be involved in this research study. Include the number of sessions and the duration of each session - consider the total number of minutes, hours, days, months, years, etc.

Participants will be enrolled in the study for 6 months. Most study visits will occur in conjunction with regular well child care, adding ~15 minutes to each visit.

8.0 Number of Subjects and Statistical Plan

8.1 Number of Subjects

Indicate the maximum number of subjects to be accrued/enrolled. Distinguish between the number of subjects who are expected to be enrolled and screened, and the number of subjects needed to complete the research procedures if applicable (i.e., numbers of subjects excluding screen failures.)

For this pilot study, 60 infants will be recruited. We believe that this number of infants who meet the inclusion/exclusion criteria can feasibly be recruited over a 6 month period.

8.2 Sample size determination

If applicable, provide a justification of the sample size outlined in section 8.1 to include reflections on, or calculations of, the power of the study.

The sample size for this pilot study is based upon the number of participants that we felt we could feasibly recruit given the time and resources available for recruitment. As this pilot is going to determine feasibility, 60 participants should be adequate. Further, we will use the data generated to determine the sample size necessary for a fully powered subsequent trial.

8.3 Statistical methods

Describe the statistical methods (or non-statistical methods of analysis) that will be employed.

We will assess conditional weight gain from birth to 6 months to assess rapid infant growth.^{80,81} Conditional weight gain will be calculated as standardized residuals from the linear regression of weight for age at 6 months on weight for age at birth, with length for age at birth and 6 months and infant age at the 6-month visit entered as covariates. We will explore the moderating role of child sex, delivery mode, and maternal parity on intervention effects. Similar analyses will be conducted for the intervention period spanning ages 1-6 months.

For cross-sectional analyses at age 6 months, ANOVA will estimate the effects of intervention group on mean weight-for-length. Logistic regression will be used to compare intervention effects on the dichotomous outcome of overweight at 6 months.

For growth from 1-6 months, we will fit a repeated measures ANOVA of BMI, with visit and study group as within and between factors, respectively.

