1.0 Objectives

1.1 Study Objectives

Describe the purpose, specific aims or objectives. State the hypotheses to be tested.

This pilot study seeks to determine if formula feeding recommendations that are calibrated using age and weight specific caloric intake recommendations can prevent excessive infant weight gain and reduce overweight in the first 6 months after birth among infants born to mothers with overweight prior to pregnancy electing to exclusively formula feed their infants. Calibrated formula feeding refers to adjusting the recommended daily caloric formula intake to account for weight status. A cohort of 60 infants will be recruited and randomized 2-3 weeks after birth to an intervention arm characterized by calibrated formula feeding recommendations or a control group with ad lib feeds as per usual care. Intervention group parents will also be given written instructions on infant hunger and satiety cues as well as copies of videos with guidance on bottle feeding and how to soothe fussy infants without feeding. We hypothesize that the calibrated formula intake intervention will reduce rapid infant gain and overweight during infancy resulting in lower weight-for-length at age 6 months.

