1.3 Secondary Study Endpoints

State the secondary endpoints to be measured in the study.

- Conditional Weight Gain during the intervention period spanning Ages 1-6 Months
- Mean Weight-for-Length Z-score (WLZ) at Age 6 Months
- Growth Trajectory during the intervention period spanning Ages 1-6 Months (repeated measures of weight-for-length)
- Proportion of Infants with Overweight (Weight-for-Length $\geq 95^{\text{th}}$ Percentile on WHO Growth Charts) at Age 6 months
- Feasibility: a) recruitment, b) ability to give tailored formula volume recommendations, c) visit completion, d) retention through 6 months
- Acceptability: parent adherence to formula volume recommendations as measured by 3 day feeding diaries at 2, 3, 4, 5, and 6 months for the intervention group

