7.2 Study Procedures

Provide a step by step description of all research procedures being conducted (broken down by visit, if applicable) including such information as below (where and when applicable); describe the following:

- HOW: (e.g., data collection via interviews, focus groups, forms such as surveys and questionnaires, medical/school records, audio/video/digital recordings, photographs, EKG procedures, MRI, mobile devices such as electronic tablets/cell phones, observations, collection of specimens, experimental drug/device testing, manipulation of behavior/use of deception, computer games, etc.)

- WHERE: (e.g., classrooms, labs, internet/online, places of business, medical settings, public spaces, etc.)

Prior to enrollment, infants will be screened by study coordinators to ensure eligibility consistent with study inclusion/exclusion criteria.

7.2.1 Visit 1

Provide a description of what procedures will be performed on visit 1 or day 1 or pre-test in order of how these will be done. If your study only involves one session or visit, use this section only and indicate 7.2.2 as not applicable.

Birth – infant age 1 month: Parents will then review and complete the informed consent document during the birth hospitalization or at a clinic visit allowing for continued participation. Demographic data will be collected from parent-completed surveys on Redcap. Study coordinators will review the electronic medical record to obtain data related to pregnancy and birth history (e.g. birthweight, gestational age, maternal pre-pregnancy BMI, etc.). Additionally, parent contact information will be obtained.

Anthropometrics – if enrollment occurs during the birth hospitalization, birth weight and birth length will be recorded from the electronic medical record. If enrollment occurs at an outpatient clinic visit, the following procedures will be used (and for all subsequent weights and lengths):

- Weight – will be measured to the nearest 0.001 kg using a calibrated, digital electronic scale
- Recumbent Length – will be measured to the nearest 0.1 cm using a portable stadiometer (Shorr)

Diary card - Parents will be given a diary card to record volume of infant formula consumed for the 3 days prior to the 1 month well child visit (Visit 2) and all subsequent visits. Instructions for the diary card will ask parents:

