- a) Volume consumed in each feeding for the day (volume is the amount that passes the infant's lips – if formula is spit-up, it still counts as having been consumed)
- b) Type of infant formula
- c) Size of bottle used
- d) Other sources of nutrition (e.g. juice, water, foods)

Randomization – following the visit, infants will be randomized to intervention or control using a computer-generated randomization program generated by a statistician not affiliated with the trial. Randomization will include stratification for sex of the infant (male/female) and maternal pre-pregnancy BMI category ($25-29.9 \text{ kg/m}^2$ vs. $\geq 30 \text{ kg/m}^2$).

7.2.2 Visit 2

Provide a description of what procedures will be performed on visit 2 or day 2 or post-test in order of how these will be done. If your study involves more than two sessions or visits replicate this section for each additional session or visit (e.g., 7.2.3, 7.2.4, etc.).

Age 1 Month Visit (ages 24 – 41 days)

Both study groups:

1. Anthropometrics of infant (weight, recumbent length)
2. Parent-completed Surveys
 - a. Baby Eating Behavior Questionnaire⁷⁶
 - b. Babies Basic Needs Questionnaire

- c. Single item adapted from the Infant Feeding Practices Study II⁷⁷: “I encourage my infant to finish his or her bottle of formula”⁷⁸; responses include:
Never Rarely Sometimes Most of the time Always.....
- 3. Diary cards to be completed for the 3 days following the visit
- 4. Diary cards to be completed x 3 days prior to next study visit

Intervention group only:

1. Parents will be provided with handouts on hunger/satiety cues and calming a fussy baby
2. Parents will be given a digital streaming copy of the video, “Happiest Baby on the Block” available at: <https://www.happiestbaby.com/products/baby-streaming-video-english>
3. Parents will be given a copy of a video demonstrating responsive bottle feeding: <https://youtu.be/NLnPGJKdPUw>⁷⁸
4. Parents will be given a copy of Bottle Feeding Basics video: <https://360.articulate.com/review/content/99a63b9a-184c-474e-b836-7d8cd8aa1652/review>
5. Study coordinators will provide parents with a range of formula volume to be consumed based upon research conducted by Butte:⁷⁹

Table 8 Energy requirements for formula-fed infants 0–12 months of age

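### The 6-month weight-for-length comparison names no starting value as a covariate; adding birth WLZ and the stratification factors would gain precision at almost no cost

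*Combined protocol and SAP*

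**What the plan says.** The hypothesis in section 1.1 ends with the intervention "resulting in lower weight-for-length at age 6 months". Section 1.3 lists the matching secondary endpoint as "Mean Weight-for-Length Z-score (WLZ) at Age 6 Months". In section 8.3 the analysis is one sentence: "ANOVA will estimate the effects of intervention group on mean weight-for-length". It names no starting value and neither of the two stratification factors given under Visit 1 in section 7.2 (infant sex and maternal pre-pregnancy BMI category).

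The same section does name covariates for the primary endpoint. Conditional weight gain is taken as "standardized residuals from the linear regression of weight for age at 6 months on weight for age at birth". That model also adjusts for the infant's length at both time points and for exact age at the final visit.

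Starting size is therefore needed for the primary model in any case. For infants enrolled in hospital, section 7.2.1 states that "birth weight and birth length will be recorded from the electronic medical record". For infants enrolled at a clinic, weight and length are measured at that visit. Both arms are weighed and measured again at Visit 2 (24–41 days).

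On timing, section 7.2.1 states that "following the visit, infants will be randomized to intervention or control", where the visit is Visit 1. The intervention materials and volume recommendations are first given at Visit 2.

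**The concern.** An infant's weight-for-length at 6 months can be expected to depend partly on where the infant started. A comparison on group alone leaves that variation in the error term, so its interval is wider than the collected data require. With about 30 infants per arm, the arms can also differ by chance at the start. Entry restricts birthweight (section 3.1) but not weight-for-length, and randomisation is not stratified on it.

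The plan conditions on starting size for the primary endpoint and not here, and it gives no reason for the difference. Two things are at stake. One is the precision of the estimate that answers the closing clause of the hypothesis. The other is the use of the pilot data to size the next trial (section 8.2). If that trial adjusts for a starting value, it needs the adjusted residual SD, which a group-only ANOVA does not produce.

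**Working it through.** **Figure to reproduce.** None. Section 8.2 sets 60 infants by feasibility and states no power, effect size, SD or alpha.

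**Inputs**
- Total of 60 infants (section 8.1). The allocation ratio is not stated; 1:1 is assumed, so n = 30 per arm.
- SD of 6-month WLZ is taken as 1 unit, so all results are in SD units (assumption).
- Correlation ρ between starting and 6-month WLZ is not in the documents; the range 0.2 to 0.7 is assumed.
- No expected attrition is given. The only figure is the 33% suspension trigger in section 9.8, so 20 per arm is used as a low case.

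**Formulas**
- Unadjusted SE = √(2/n) = √(2/30) = 0.258.
- Adjusted SE = √(1 − ρ²) × √(2/n).
- Variance reduction = ρ².
- Equivalent unadjusted sample = 60/(1 − ρ²).
- Shift in the unadjusted estimate from a starting imbalance of 0.3 SD = 0.3 × ρ.

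| ρ | Variance cut | Adjusted SE | Equivalent infants | Shift from 0.3 SD imbalance |
|---|---|---|---|---|
| 0.2 | 4% | 0.253 | 62.5 | 0.06 |
| 0.3 | 9% | 0.246 | 65.9 | 0.09 |
| 0.5 | 25% | 0.224 | 80.0 | 0.15 |
| 0.7 | 49% | 0.184 | 117.6 | 0.21 |

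At ρ = 0.5 the 95% CI half-width falls from 0.517 to 0.448 SD. At 20 per arm the SE falls from 0.316 to 0.274.

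**How often an imbalance arises.** The starting difference between arms also has SD 0.258. The chance that it exceeds 0.3 SD in either direction is 2 × [1 − Φ(0.3/0.258)] = 0.245, about 25%. For 0.5 SD it is about 5%. At 20 per arm the two figures are 34% and 11%.

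**Check by simulation** (20,000 trials, 30 per arm, no true effect)
- Both methods averaged within about 0.003 of zero at every ρ tried, so neither is biased.
- The SD of the estimate, ANOVA against ANCOVA, was 0.258 against 0.250 (ρ = 0.3), 0.258 against 0.225 (0.5) and 0.261 against 0.188 (0.7).
- At ρ = 0 it was 0.259 against 0.261, so adjusting for a useless covariate costs about 1%.
- In trials with a starting imbalance near 0.3 SD, ANOVA was shifted by 0.077, 0.147 and 0.201 at ρ = 0.3, 0.5 and 0.7. ANCOVA stayed within 0.02 of zero.

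These figures count the starting value only. They credit no gain from the stratification factors.

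**Which starting value.** Randomisation follows Visit 1. Section 1.1 puts it at 2–3 weeks after birth, and section 7.1 between birth and 1 month. Visit 2 is at 24–41 days. Birth WLZ therefore precedes allocation. The 1-month WLZ comes after allocation, although before any recommendation is given.

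**The case against.** Four objections have force.

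1. **No bias.** A reader might infer that the unadjusted comparison is biased, or that a starting imbalance passes into it in full. The documents support neither reading. Allocation is randomised, the ordinary interval already allows for chance imbalance, and only a share equal to ρ carries through. This stands, and it limits the point to precision and to the estimate in a particular unbalanced trial.

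2. **The 1-month value is not a clean baseline.** It is tempting to adjust for WLZ at Visit 2, because the intervention starts there. That value follows randomisation, and no blinding of parents is described. This stands. It is also why birth WLZ should not fill gaps in a 1-month covariate: the two are measured at different ages, the birth length may come from the medical record and later lengths from a stadiometer, and their correlations with the outcome need not match.

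3. **The gain is unknown.** The documents do not give ρ. Entry at or above the 50th birthweight percentile may narrow the starting range and lower ρ, and an intervention that changes with weight-for-length may weaken tracking in that arm. This stands. At ρ = 0.2 the variance falls by only 4%.

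4. **Limited consequence.** This is a secondary endpoint in a feasibility pilot with no power target. The primary endpoint already conditions on birth size, and the repeated measures analysis includes the 1-month visit. This stands as to weight, but neither of those analyses adjusts the 6-month WLZ contrast.

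It is also fair to say that a group-only model is inferred from silence. Since section 8.3 lists covariates for the primary endpoint, that is the natural reading. If a covariate was intended, it still needs to be written down.

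**Conclusion.** The point holds as a precision improvement to a secondary endpoint; it is a free improvement, not a flaw that threatens validity. With 30 per arm and ρ between 0.2 and 0.7, adjustment reduces the variance of the 6-month WLZ contrast by 4% to 49%, and by 25% at ρ = 0.5. The size rests on an assumed correlation, 1:1 allocation and all 60 infants being analysed. For birth WLZ the lower part of the range is plausible, given the restriction on birthweight and lengths taken from the record.

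A reader might conclude that the planned ANOVA would give a wrong answer or that the primary result is affected. Neither follows: the contrast is unbiased under randomisation, and the primary endpoint is a different analysis that already uses birth size.

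**What to change.** Replace the sentence in section 8.3 with:

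> 6-month WLZ will be compared by ANCOVA with study group, birth WLZ (pre-randomisation) and the stratification factors (infant sex, maternal BMI category) as covariates; the adjusted difference and 95% CI will be reported.

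Add one sensitivity analysis with 1-month WLZ as the starting covariate in place of birth WLZ, and state that it is measured after randomisation but before any recommendation is given. Do not substitute one baseline for the other in infants who lack a value. Naming WLZ also brings section 8.3 into line with section 1.3.

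State that birth length will be taken from the record for every infant, including those enrolled at a clinic; the primary model already requires it. Report the residual SD from the adjusted model for planning the next trial.

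**Cost.** One or two sentences and no new measurements. With all 60 infants analysed, the residual degrees of freedom fall from 58 (60 − 2) to 55 (60 − 5). If the correlation proves low, the gain is small; at zero correlation, adjusting for the starting value costs about 1% in precision.

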3.3.2 Follow-up for withdrawn subjects

Describe when and how to withdraw subjects from the study; the type and timing of the data to be collected for withdrawal of subjects; whether and how subjects are to be replaced; the follow-up for subjects withdrawn from investigational treatment.

Study personnel will contact consenting parents by phone notifying them of their removal from the study and the reason for withdrawal. If the reason is due to failure-to-thrive, the infant's pediatrician will also be notified. If study personnel are unable to reach the consenting parent, a letter will be sent via US mail.

No further data will be collected on participants that are withdrawn, and these participants will not be replaced.

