9.8 Suspension of research

Describe any conditions that trigger an immediate suspension of research.

Suspension of the research would occur if:

1. >33% of participants are not adhering to the data collection procedures
2. >33% of intervention group participants meet criteria for failure-to-thrive
3. Attrition exceeds 33% after Visit 2

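### The logistic regression planned for overweight at 6 months has no sparse-data provision, and at about 30 infants per arm an arm with no events is a real possibility if the event rate is low

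*Combined protocol and SAP*

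**What the plan says.** Section 1.3 lists "Proportion of Infants with Overweight" as a secondary endpoint, defined as weight-for-length at or above the 95th WHO percentile at 6 months. Section 8.3 gives its analysis in one sentence: "Logistic regression will be used to compare intervention effects on the dichotomous outcome of overweight at 6 months". It names no covariates, penalised or exact version, method of inference (Wald, likelihood ratio or profile), or rule for an arm without events.

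On numbers, section 8.1 says "For this pilot study, 60 infants will be recruited", and section 8.2 explains that the size is "based upon the number of participants that we felt we could feasibly recruit given the time and resources available for recruitment". No event rate or effect size is given. Section 7.2 says that "infants will be randomized to intervention or control using a computer-generated randomization program", stratified by infant sex and maternal BMI category, without stating the ratio.

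On losses, section 3.3.2 says "No further data will be collected on participants that are withdrawn, and these participants will not be replaced". Section 9.8 lists "Attrition exceeds 33% after Visit 2" among the conditions for suspending the research.

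**The concern.** By construction, a 95th-percentile cut-off marks about 5% of the reference population. With 30 infants in an arm, a 5% rate gives 30 × 0.05 = 1.5 expected events and a 15% rate gives 4.5. At counts this low an arm can end with none.

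Ordinary logistic regression then has no finite estimate. If one arm is empty, the fitted odds ratio runs to zero or infinity, the standard error becomes enormous and the Wald p-value goes towards 1. Standard software may still print these values as a result.

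The stated hypothesis includes a reduction in overweight, and the lower the intervention-arm rate, the likelier that arm is to be empty. Section 8.2 also says that the data will be used to size a later trial. An infinite or zero odds ratio is no help for that, and a replacement method chosen after the empty cell has been seen is a post hoc choice.

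**Working it through.** The plan states no figure for this endpoint, so there is none to reproduce.

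**Inputs**
- Total of 60 infants (section 8.1). The split of 30 per arm assumes 1:1 allocation.
- Lower bound of 20 per arm: one third lost, the level that section 9.8 treats as the limit, leaves about 40 of 60. This is a bound, not a forecast.
- Event rates: not in the documents. Assumed control rates run from 5% to 30%, with the intervention rate either equal or halved. The nearest figure in the protocol is 9–14% obese at ages 2–5 years (section 2.3). That is a different age group and only a guide.

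**Chance of an empty arm**

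For one arm with true rate p and n infants analysed, P(no events) = (1 − p)^n. With a and b for the two arms, P(at least one empty) = a + b − ab.

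Example, 10% control and 5% intervention, n = 30: a = 0.90^30 = 0.042 and b = 0.95^30 = 0.215, so a + b − ab = 0.042 + 0.215 − 0.009 = 0.248.

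| Control / intervention rate | 30 per arm | 25 per arm | 20 per arm |
|---|---|---|---|
| 5% / 5% | 38% | 48% | 59% |
| 10% / 5% | 25% | 33% | 44% |
| 15% / 7.5% | 10% | 16% | 24% |
| 20% / 10% | 4% | 8% | 13% |
| 30% / 15% | 1% | 2% | 4% |

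The 5%/5% row is a no-effect case. It includes a 4.6% chance (30 per arm) that both arms are empty, which leaves the odds ratio undefined.

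**Where it becomes material.** Setting (1 − p)^n = 0.10 gives p = 1 − 0.10^(1/n), which is 7.4% for n = 30, 8.8% for n = 25 and 10.9% for n = 20. So at 30 per arm the risk is about 10% or more once the intervention rate is about 7.5% or lower. If 9–14% were the control rate and the intervention halved it, the risk would be 30% down to 12% at 30 per arm, and 49% down to 27% at 20 per arm.

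**What the fit returns.** Take 0/30 (intervention) against 6/30 (control):
- Ordinary logistic regression: log odds ratio about −22, standard error about 14,500, Wald p = 0.999.
- Likelihood-ratio test from the same model: p = 0.003. Profile upper limit for the odds ratio: 0.32. There is no finite lower limit.
- Fisher exact test: p = 0.024.
- Risk difference: −20 points, Newcombe 95% CI −37 to −5.
- Firth odds ratio (for a 2×2 table, 0.5 added to each cell): (0.5 × 24.5)/(30.5 × 6.5) = 0.062. A Wald-type interval around it runs from 0.003 to 1.15, which is why a profile-likelihood interval is preferable.

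**Check on the alternative.** Full enumeration of the 2×2 tables at 30 per arm gives Newcombe coverage of 99%, 98%, 96%, 96% and 95% for the five rows above. At 0/30 against 5/30 the Newcombe interval is −34 to −2 points, but Fisher p = 0.052, so the two can disagree.

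**The case against.** The size of the risk rests wholly on an event rate that the documents do not give. A reader might infer that an empty arm is a material risk at any plausible rate. The table does not support that: with 30 per arm the risk is 4% at 20/10% and 1% at 30/15%. These infants are selected for risk (maternal BMI of at least 25, birthweight at or above the 50th percentile, formula feeding), so their control rate may well exceed the reference 5%. The 38% figure pairs that unselected rate with no effect, so it does not illustrate a successful intervention. This objection stands, and it limits the size of the claim.

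A reader might also infer that logistic regression yields nothing usable with an empty arm. That goes too far. The likelihood-ratio test and a one-sided profile bound survive, and section 8.3 does not commit to Wald inference. It does not name either alternative, however, and the likelihood-ratio test is liberal at these counts (0.003 against Fisher's 0.024).

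A third tempting inference is that the stratification factors make separation likelier. Section 7.2 uses them for randomisation only, and section 8.3 does not put them in this model.

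Finally, this is one of several secondary endpoints in a pilot sized for feasibility. Events per arm can be reported whatever the model does, and an analyst would notice a zero. That is true, but the replacement would then be chosen with the data in view.

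**Conclusion.** The point holds as a cheap improvement to one secondary analysis. With 1:1 allocation and 30 infants analysed per arm, the chance of at least one empty arm is 10% to 38% at assumed control/intervention rates from 15/7.5% down to 5/5%, and 1% to 4% at rates from 30/15% to 20/10%. Losses raise it: at 20 per arm the five scenarios give 4% to 59%. The direction is plain arithmetic: with the control rate fixed, a lower intervention rate makes an empty arm likelier.

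If an arm is empty, the odds ratio and the default Wald results are lost, though not every form of inference from the model. The primary endpoint (conditional weight gain, a continuous measure) and the feasibility endpoints do not depend on this. How often the problem would arise cannot be settled from the documents, because the event rate is an assumption throughout.

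**What to change.** Replace the logistic regression sentence in section 8.3 with wording to this effect:

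*Overweight at 6 months will be reported as the number of events and infants analysed in each arm. The governing estimate is the risk difference with a Newcombe (score) 95% confidence interval. Any odds ratio will come from Firth penalised logistic regression with a profile-likelihood interval. Any exact test is supportive only.*

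The last sentence is needed because the interval and Fisher's test can fall on different sides of the 5% line, as at 0/30 against 5/30.

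The cost is a few lines of text. No new data are needed and nothing changes for participants. The small statistical price is slightly conservative intervals when events are few (coverage of 96–99% at 30 per arm for the scenarios from 20/10% down to 5/5%). If both arms have no events, no method can estimate a ratio, but the risk difference still has an interval (about ±11 points at 0/30 against 0/30).

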3.3 Early Withdrawal of Subjects

3.3.1 Criteria for removal from study

Insert subject withdrawal criteria (e.g., safety reasons, failure of subject to adhere to protocol requirements, subject consent withdrawal, disease progression, etc.).

1. Infants exhibiting failure-to-thrive defined as:
 - a. Weight-for-length $< 5^{\text{th}}$ percentile for sex and age on the WHO growth chart
 - b. Downward crossing of > 2 major centile lines on the WHO growth chart (relevant major lines include 95th, 90th, 75th, 50th, 25th, 10th, 5th) after enrollment
2. Non-adherence to the study visit schedule characterized by failing to complete **two** scheduled study intervention visits within 2 weeks of turning 1, 2, 3, 4, and 5 months old (does not include enrollment and final visit)

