7.1 Study Design

Describe and explain the study design.

This study is a randomized, clinical trial involving 60 exclusively formula fed infants born at ≥ 37 weeks gestational age who are at-risk for overweight based upon maternal pre-pregnancy overweight or obesity (or alternatively at first prenatal visit if pre-pregnancy weight/height not known) and infant birthweight $\geq 50^{\text{th}}$ percentile. Infants will be enrolled at Penn State Health Children's Hospital or at affiliated clinics within the Division of Academic General Pediatrics between birth and age 1 month, where they will be randomized to a calibrated formula intake intervention or control. Participating infants in the intervention group will be seen monthly until age 6 months where they will be weighed and measured, and parents will complete surveys related to volume of formula consumed, infant appetite, parent feeding style, and infant temperament. Control infants will follow the same procedures, but will not have scheduled visits at ages 3 and 5 months. Instead their visits will correspond to usual care well child visits at ages 1, 2, 4, and 6 months.

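### The 1–6 month growth trajectory is defined as weight-for-length (section 1.3) but analysed as BMI (section 8.3), by a method that would normally drop infants missing one visit

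*Combined protocol and SAP*

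**What the plan says.** Section 1.3 lists among the secondary endpoints "Growth Trajectory during the intervention period spanning Ages 1-6 Months (repeated measures of weight-for-length"), and separately "Mean Weight-for-Length Z-score (WLZ) at Age 6 Months". The hypothesis in section 1.1 also ends on this measure: "resulting in lower weight-for-length at age 6 months".

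Section 8.3 treats the two endpoints differently. At month 6, "ANOVA will estimate the effects of intervention group on mean weight-for-length". For growth over months 1–6, "we will fit a repeated measures ANOVA of BMI, with visit and study group as within and between factors, respectively". It does not list the visits, say whether BMI is raw or a z-score, name the contrast of interest, or say what happens to an infant with an incomplete series.

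The arms have different schedules. Section 7.1 has the intervention arm seen monthly to 6 months. Controls have no month 3 or 5 visit: "Instead their visits will correspond to usual care well child visits at ages 1, 2, 4, and 6 months".

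Under section 3.3.1 an infant is removed for non-adherence after failing to complete two "scheduled study intervention visits within 2 weeks of turning 1, 2, 3, 4, and 5 months old"; enrolment and the final visit do not count. Once an infant is removed, section 3.3.2 applies: "No further data will be collected on participants that are withdrawn, and these participants will not be replaced".

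**The concern.** Endpoint and analysis name different variables. Both come from weight and length, but WHO weight-for-length relates weight to length, while BMI divides weight by length squared and is usually referenced to age. The two can rank the same infants differently. Nothing in the protocol says that BMI stands in for weight-for-length, and infant BMI appears in no endpoint, procedure or other analysis. With both measures in the plan, the choice between them could be made after the data are seen.

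The second issue is the method. In its standard form a repeated-measures ANOVA needs a full set of visits for every infant. The withdrawal rule deliberately keeps infants who miss one visit, so the analysis could discard infants whom the trial retained, along with measurements already taken. With 60 infants that may matter, and section 8.2 says that these data will be used to size the next trial.

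**Working it through.** **1. Endpoint against analysis (no arithmetic).**

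| Place | Infant measure |
|---|---|
| 1.1, hypothesis | weight-for-length at month 6 |
| 1.3, month-6 mean | weight-for-length z-score |
| 1.3, overweight | weight-for-length percentile |
| 1.3, trajectory | weight-for-length, repeated |
| 7.2.2, 75th-percentile feeding rule | weight-for-length |
| 8.3, month-6 ANOVA | weight-for-length |
| 8.3, trajectory ANOVA | **BMI** |

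Only the last row differs.

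**2. Visits available to both arms.** Intervention {1, 2, 3, 4, 5, 6}; control {1, 2, 4, 6}. The intersection is {1, 2, 4, 6}. With a six-level visit factor no control could be a complete case.

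**3. Complete cases on the four shared visits.** The plan gives no figure to reproduce and no miss rate. From the documents: 60 infants (8.1), the two schedules (7.1) and removal after two missed visits among months 1–5 (3.3.1). Assumed: 30 per arm, the removal rule applied in both arms, and independent misses at rate m per visit, with m = 5% or 10%.

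- Control, complete: (1−m)^4.
- Intervention, complete: (1−m)^4 × (1−m²). The second factor excludes infants removed for missing both month 3 and month 5.

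| | m = 5% | m = 10% |
|---|---|---|
| Control | 0.8145 × 30 = 24.4 | 0.6561 × 30 = 19.7 |
| Intervention | 0.8145 × 0.9975 × 30 = 24.4 | 0.6561 × 0.99 × 30 = 19.5 |
| Complete, of 60 | 48.8 | 39.2 |
| Dropped | 11.2 | 20.8 |

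**4. Dropped infants who were retained and measured at month 6.** These miss exactly one of months 1, 2 and 4, are not removed, and attend month 6.

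- Control: 3m(1−m)^3.
- Intervention: 3m(1−m)^5, because months 3 and 5 must also be attended or the infant would be removed.

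| | m = 5% | m = 10% |
|---|---|---|
| Control | 0.1286 × 30 = 3.86 | 0.2187 × 30 = 6.56 |
| Intervention | 0.1161 × 30 = 3.48 | 0.1771 × 30 = 5.31 |
| Total | 7.3 | 11.9 |

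A wider count of dropped infants who were never formally removed gives 10.3 and 17.5. Of these, 3.0 and 5.7 miss month 6 itself, which the removal rule does not count. I therefore use about 7 and 12.

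**5. Opposite extreme.** If all misses fall in the same infants, 0.95 × 60 = 57 or 0.90 × 60 = 54 are complete. The others contribute nothing to either method, so a mixed model gains nothing.

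**6. Precision (illustration only).** Trials of 60 infants were simulated with SD 1, independent misses, no failure-to-thrive withdrawal, and correlation either exchangeable at 0.7 or AR(1) at 0.85 per month. The quantity is the standard error of the arm difference in change from month 1 to month 6, complete-case fit divided by mixed model. The ratios were 1.07 and 1.09 at 5% misses, and 1.15 and 1.18 at 10%. A recalculation with known covariance, using only the four shared visits, gave 1.07, 1.09, 1.14 and 1.18. With step 5 as the lower end, the range is 0–18%.

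**The case against.** The sentence in section 8.3 is introduced as the analysis of growth from 1 to 6 months, so it plainly targets the trajectory endpoint. A reader might infer that the endpoint is left without any analysis. The documents do not support that: an analysis is planned, with the wrong index. This part of the objection stands.

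The visit set can be worked out. If only four visits permit a between-arm comparison, section 7.1 already determines them. That also stands, so listing the visits is a clarification and not a separate defect.

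Complete-case fitting is an inference. Section 8.3 names no software or missing-data rule, and the term repeated-measures ANOVA is sometimes used loosely for likelihood-based fits that keep incomplete series. The loss is therefore conditional on the standard form of the method. The silence on incomplete series remains a gap either way.

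The month-6 comparison is protected, because section 8.3 has a separate month-6 ANOVA of weight-for-length that needs no complete series. This stands and confines the loss to the trajectory analysis.

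A reader might also infer that withdrawal for failure-to-thrive, with no further data, biases the trajectory result. The documents give no rate by arm, section 9.7 expects adverse events to be infrequent, and the month-6 ANOVA shares the same loss. No bias claim is made here.

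What the objection does not reach is the mismatch itself: no section reconciles BMI with weight-for-length.

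**Conclusion.** The mismatch is definite and needs no assumption: the secondary endpoint stated in section 1.3 is not the variable tested in section 8.3. It should be corrected. It touches neither the primary endpoint nor the sample size, which section 8.2 sets by feasibility.

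The missed-visit problem is real but conditional. If the ANOVA is fitted in its standard form and misses are independent at 5% or 10%, about 49 or 39 of 60 infants are used, and about 7 or 12 who were retained and measured at month 6 are lost. If misses cluster, 57 or 54 are used and nothing is recoverable.

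The loss of precision should not be read as an established 7–18%. It is 0–18%, holds only for the contrast in change from month 1 to month 6, and depends on assumed miss rates and correlations.

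**What to change.** In section 8.3:

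1. Replace BMI with WHO weight-for-length z-score.
2. Name months 1, 2, 4 and 6 as the visits. Adding months 3 and 5 to an arm-by-visit model would leave two empty control cells.
3. Fit a linear mixed model to all available measurements at those visits, with arm, visit, arm-by-visit, infant sex and maternal BMI category (the last two are the randomisation stratifiers in section 7.2.1).
4. State the contrast: arm difference in change from month 1 to month 6.
5. Name a simpler fallback covariance, for example random intercept and slope.

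If the ANOVA is kept, the minimum is to state the z-score outcome and the four visits, and to report the infants excluded by arm and reason.

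The cost is a few sentences of wording and slightly more analysis work, with no new data or visits. An unstructured covariance may not converge with 60 infants, hence the fallback.
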